9.3.4 Adherence and Retention Analyses

Adherence will be defined as patients completing their post-operative visits at the following intervals: 1 week, 4-6 weeks, 3 months, 6 months, 9 months, and 12 months.

9.3.5 Baseline Descriptive Statistics

Intervention groups will be compared on baseline characteristics, including demographics and laboratory measurements, using descriptive statistics. These characteristics will be compared at baseline (pre-operative time point) and at final follow-up.

9.3.6 Planned Interim Analysis

Not applicable.

CONFIDENTIAL

This material is the property of the NYU School of Medicine and Langone Medical Center. Do not disclose or use except as authorized in writing by the study sponsor

9.3.7 Additional Sub-Group Analyses

Not applicable.

9.3.8 Multiple Comparison/Multiplicity

Not applicable.

9.3.9 Tabulation of Individual Response Data

Individual participant data will be recorded by measure and time point, but will be reported in literature as means and standard deviations.

9.3.10 Exploratory Analyses

Not applicable.

9.4 Sample Size

Based on an effect size of 0.25 with 3 cohorts, a total of 159 patients are needed with 53 in each group. Assuming a 15% drop-out/lost to follow up rate, each group will enroll 60 patients. Outcome measures will include patient reported outcomes: VAS, KOOS, Kujala, and IKDC. Additionally, we will report on rates of complications post-operatively, if any. Type I error rate (alpha) will be set at 0.05. Power will be set at 0.80.

10 Source Documents and Access to Source Data/Documents

Source data is all information, original records of clinical findings, observations, or other activities in a clinical trial necessary for the reconstruction and evaluation of the trial. Source data are contained in source documents. Examples of these original documents, and data records include: hospital records, clinical and office charts, laboratory notes, memoranda, subjects' diaries or evaluation checklists, pharmacy dispensing records, recorded data from automated instruments, copies or transcriptions certified after verification as being accurate and complete, microfiches, photographic negatives, microfilm or magnetic media, x-rays, subject files, and records kept at the pharmacy, at the laboratories, and at medico-technical departments involved in the clinical trial. It is acceptable to use CRFs as source documents. If this is the case, it should be stated in this section what data will be collected on CRFs and what data will be collected from other sources.

The study case report form (CRF) is the primary data collection instrument for the study. All data requested on the CRF must be recorded. All missing data must be explained. If a space on the CRF is left blank because the procedure was not done or the question was not asked, write "N/D". If the item is not applicable to the individual case, write "N/A". All entries should be printed legibly in black ink. If any entry error has been made, to correct such an error, draw a single straight line through the incorrect entry and enter the correct data above it. All such changes must be initialed and dated. DO NOT ERASE OR WHITE OUT ERRORS. For clarification of illegible or uncertain entries, print the clarification above the item, then initial and date it.

Access to study records will be limited to IRB-approved members of the study team. The investigator will permit study-related monitoring, audits, and inspections by the IRB/EC, the sponsor, government regulatory bodies, and University compliance and quality assurance groups of all study related documents (e.g. source documents, regulatory documents, data collection instruments, study data etc.). The investigator will ensure the capability for inspections of applicable study-related facilities (e.g. pharmacy, diagnostic laboratory, etc.).

Participation as an investigator in this study implies acceptance of potential inspection by government regulatory authorities and applicable University compliance and quality assurance offices.

CONFIDENTIAL

This material is the property of the NYU School of Medicine and Langone Medical Center. Do not disclose or use except as authorized in writing by the study sponsor

11 Quality Assurance and Quality Control

QC procedures will be implemented beginning with the data entry system and data QC checks that will be run on the database will be generated. Any missing data or data anomalies will be communicated to the site(s) for clarification/resolution.

Following written SOPs, the monitors will verify that the clinical trial is conducted and data are generated, documented (recorded), and reported in compliance with the protocol, GCP, and the applicable regulatory requirements (e.g., Good Laboratory Practices (GLP), Good Manufacturing Practices (GMP)).

The investigational site will provide direct access to all trial related sites, source data/documents, and reports for the purpose of monitoring and auditing by the sponsor, and inspection by local and regulatory authorities.

12 Ethics/Protection of Human Subjects

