3.1 Description of Study Design

This will be a single-center randomized controlled study. Patients will be randomized using RedCap using simple randomization. The study is comparing postoperative anterior knee pain after ACLR with BPTB autograft. There will be three cohorts that differ base on the bone-void filler used in the patellar boney defect. The three cohorts will include 1) autogenous bone obtained from the BTBPB graft harvest 2) Autologous bone plus demineralized bone matrix (Allosync DBM Putty, Arthrex, Naples, FL) and 3) autologous bone plus calcium phosphate cement (Quickset, Arthrex, Naples, FL).

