4.6 Total Number of Participants and Sites

Based on an effect size of 0.25 with 3 cohorts, a total of 159 patients are needed with 53 in each group. Assuming a 15% drop-out/lost to follow up rate, each group will enroll 60 patients for a total n of 180 subjects.

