9.3.2 Analysis of the Primary Efficacy Endpoint(s)

To compare primary outcomes (anterior knee pain), an analysis of variance (ANOVA) will be performed, with a p-value of 0.05 set to determine statistical significance. Testing will be performed to determine whether sample distribution is normal; if not, non-parametric testing will be performed. Patients who do not complete at least 80% of follow-up visits will be considered lost to follow-up and will not be included in the analysis.

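### Minor: 60 per group does not cover the stated 15% loss; it leaves 51 per group (153 in total), not the 53 (159) the plan requires

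*Combined protocol and SAP*

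**What the plan says.** Section 9.4 (Sample Size) gives the base requirement: "Based on an effect size of 0.25 with 3 cohorts, a total of 159 patients are needed with 53 in each group". It adds "Type I error rate (alpha) will be set at 0.05" and "Power will be set at 0.80". The allowance for loss follows from the base requirement: "Assuming a 15% drop-out/lost to follow up rate, each group will enroll 60 patients". Section 4.6 (Total Number of Participants and Sites) repeats the requirement and gives the total: "each group will enroll 60 patients for a total n of 180 subjects".

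Two other sections bear on the point. Section 9.3.2 sets a threshold of 80% of follow-up visits and says that patients below it "will be considered lost to follow-up and will not be included in the analysis"; section 9.3.3 does the same for the secondary endpoints. Section 3.1 describes the allocation: "Patients will be randomized using RedCap using simple randomization".

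**The concern.** An allowance for loss is meant to make the number remaining after loss equal the number required. Here, the enrolment figure and the loss rate in the same paragraph leave fewer patients than that paragraph requires. A reader of 4.6 or 9.4 would take it that the trial can lose 15% of its patients and still have 159 to analyse with at least 80% power. On the plan's own figures it cannot.

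The shortfall would not matter if lost patients were kept in the primary analysis, but the plan excludes them and describes no imputation or alternative analysis set. What is at stake is the accuracy of the stated size and power, and, if the gap were large enough, the power itself.

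**Working it through.** **Inputs.** From section 9.4: effect size 0.25, three groups, alpha 0.05, power 0.80, 53 per group (159) required, 15% loss, 60 enrolled per group. From section 4.6: 180 enrolled in total. From section 9.3.2: ANOVA across the three groups, with patients counted as lost left out. The documents do not name the effect-size metric; Cohen's f is assumed.

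**1. Reproduce the plan's base figure.** For a one-way ANOVA with k = 3 groups and N analysed patients, power = P(F' > F crit). F crit is the 95th percentile of F with 2 and N - 3 degrees of freedom, and F' is noncentral F with noncentrality f² x N = 0.0625 x N.

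| N analysed | Per group | Power at f = 0.25 |
|---|---|---|
| 153 | 51 | 0.7883 |
| 156 | 52 | 0.7967 |
| 157 | – | 0.7995 |
| 158 | – | 0.8022 |
| 159 | 53 | 0.8049 |
| 180 | 60 | 0.8546 |

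The smallest N with 80% power is 158, so the smallest design with equal groups is 53 per group, 159 in total. The plan's figure reproduces exactly, which supports reading 0.25 as Cohen's f.

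**2. Apply the stated loss to the stated enrolment.** 60 x 0.85 = 51 per group; 180 x 0.85 = 153 in total. The shortfall is 159 - 153 = 6 patients, or 2 per group. This step does not depend on the effect-size metric.

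**3. Find what 60 per group does cover.** The largest loss that leaves 53 per group is 1 - 53/60 = 11.7%, or 21 of 180. The largest loss that keeps 80% power is 1 - 158/180 = 12.2%, or 22 of 180.

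**4. Find what 15% loss would need.** 53/0.85 = 62.4, so 63 per group, 189 in total. By comparison, 53 x 1.15 = 60.95, so the stated 60 may come from multiplying by 1.15 where dividing by 0.85 was needed. That origin is an inference, and nothing here depends on it.

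**5. Size the effect.** At 153 analysed, power is 0.7883: 80.0 - 78.8 = 1.2 percentage points below target. The effect detectable with 80% power at 153 is f = 0.2535, in place of 0.25.

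**The case against.** The strongest reply is that the gap has almost no practical effect. The plan gives no source for 0.25 or for 15%, so a change in the third decimal of f is finer than the inputs justify. If each of 180 patients were lost independently with probability 0.15, the analysed number would have a standard deviation of √(180 x 0.85 x 0.15) = 4.8, so a 95% range of roughly 143 to 162. A gap of six lies inside that range. This stands, and it is why the point is minor. It does not make the stated allowance correct, since the expected number is still 153.

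A second reply is that not every drop-out need leave the analysis. Of the six post-operative visits, a patient who completes five (83%) and then stops passes the 80% rule; one who completes four (67%) does not. The figure of 153 therefore assumes that all of the 15% fail the rule. That is the natural reading, because section 9.3.2 uses the same term for the patients it excludes, but the plan does not say that the two groups are identical.

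Third, the power figures depend on reading 0.25 as Cohen's f, which the sponsor should confirm. The 51 and 153 do not.

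Finally, a statement of 79% power could appear to clash with the 0.80 in section 9.4. The two are compatible if 0.80 is presented as the design target behind 159, and 79% as the power expected at 15% loss.

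**Conclusion.** The point holds and is minor. At the stated 15% loss, 60 per group leaves 51 per group and 153 in total, six fewer than the 159 that sections 4.6 and 9.4 require. Expected power is 78.8% against a target of 80%, so the trial is not materially underpowered; the written figures are simply inconsistent.

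The 153 rests on all lost patients leaving the analysis, and the power figures rest on Cohen's f and on equal groups. Under simple randomisation, 60 and 51 are expected group sizes, not fixed ones; this does not change the total of 153.

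**What to change.** Keep 180 enrolled and replace the enrolment and loss statement in both 4.6 and 9.4 with text such as:

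> About 60 patients per group (180 in total) will be enrolled. With 15% loss, about 153 are expected to be analysable (about 51 per group), giving about 79% power at Cohen's f = 0.25. The 159 analysable patients are reached if loss is no more than 11.7%.

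In 9.4, keep the alpha and outcome statements and make clear that power of 0.80 is the target from which 159 was derived. The sponsor should confirm that 0.25 is Cohen's f before the term goes into the text.

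The cost is a short edit in two sections and a slightly less favourable stated power; enrolment and conduct do not change. If the sponsor prefers to keep both 53 per group and the 15% allowance, the consistent enrolment is 63 per group (189), nine more patients. Lowering the assumed loss to 11.7% would also reconcile the figures, but only if that rate can be justified.

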12.1 Ethical Standard

The investigator will ensure that this study is conducted in full conformity with Regulations for the Protection of Human Subjects of Research codified in 45 CFR Part 46, 21 CFR Part 50, 21 CFR Part 56, and/or the ICH E6.

12.2 Institutional Review Board

The protocol, informed consent form(s), and all participant materials will be submitted to the IRB for review and approval. Approval of both the protocol and the consent form must be obtained before any participant is enrolled. Any amendment to the protocol will require review and approval by the IRB before the changes are implemented to the study. All changes to the consent form will be IRB approved; a determination will be made regarding whether previously consented participants need to be re-consented.

12.3 Informed Consent Process

12.3.1 Consent and Other Informational Documents Provided to Participants

Consent forms describing in detail the study agent, study procedures, and risks are given to the participant and written documentation of informed consent is required prior to starting intervention/administering study product. The following consent materials are submitted with this protocol: consent form, key information form.

12.3.2 Consent Procedures and Documentation

Informed consent is a process that is initiated prior to the individual's agreeing to participate in the study and continues throughout the individual's study participation. Extensive discussion of risks and possible benefits of participation will be provided to the participants and their families in a private office when they are being consented for their surgery. Consent forms will be IRB-approved and the participant will be asked to read and review the document. The investigator will explain the research study to the participant and answer any questions that may arise prior to their surgery. All participants will receive a verbal explanation in terms suited to their comprehension of the purposes, procedures, and potential risks of the study and of their rights as research participants. Participants will have the opportunity to carefully review the written consent form and ask questions prior to signing. The participants should have the opportunity to discuss the study with their surrogates or think about it prior to agreeing to participate. The participant will sign the informed consent document prior to any procedures being done specifically for the study. The participants may withdraw

CONFIDENTIAL

This material is the property of the NYU School of Medicine and Langone Medical Center. Do not disclose or use except as authorized in writing by the study sponsor

Interventional Template Version: 11 January 2019

Commented [MR5]: Edit to state that subjects will be consented prior to the day of their surgery.

Commented [EH6R5]: This has been amended

consent at any time throughout the course of the trial. A copy of the signed informed consent document will be given to the participants for their records. The rights and welfare of the participants will be protected by emphasizing to them that the quality of their medical care will not be adversely affected if they decline to participate in this study.

A copy of the signed informed consent document will be stored in the subject's research record. The consent process, including the name of the individual obtaining consent, will be thoroughly documented in the subject's research record. Any alteration to the standard consent process (e.g. use of a translator, consent document presented orally, etc.) and the justification for such alteration will likewise be documented.

12.4 Participant and Data Confidentiality

Information about study subjects will be kept confidential and managed according to the requirements of the Health Insurance Portability and Accountability Act of 1996 (HIPAA). Those regulations require a signed subject authorization informing the subject of the following:

- What protected health information (PHI) will be collected from subjects in this study
- Who will have access to that information and why
- Who will use or disclose that information
- The rights of a research subject to revoke their authorization for use of their PHI.

In the event that a subject revokes authorization to collect or use PHI, the investigator, by regulation, retains the ability to use all information collected prior to the revocation of subject authorization. For subjects that have revoked authorization to collect or use PHI, attempts should be made to obtain permission to collect at least vital status (i.e. that the subject is alive) at the end of their scheduled study period.

Data will be de-identified with a unique code and stored on password-protected computers behind the NYULH firewall as well as on REDCap, which is a HIPAA compliant and encrypted database managed by MCIT. Data will only be available to the investigators. The investigators will separately maintain the master list to reidentify subjects using RedCap.

12.5 Future Use of Stored Specimens

Not applicable, as this study does not involve the collection of samples or specimens.

13 Data Handling and Record Keeping

13.1 Data Collection and Management Responsibilities

Data collection is the responsibility of the clinical trial staff at the site under the supervision of the site PI. The investigator is responsible for ensuring the accuracy, completeness, legibility, and timeliness of the data reported.

All source documents should be completed in a neat, legible manner to ensure accurate interpretation of data. Black ink is required to ensure clarity of reproduced copies. When making changes or corrections, cross out the original entry with a single line, and initial and date the change. DO NOT ERASE, OVERWRITE, OR USE CORRECTION FLUID OR TAPE ON THE ORIGINAL.

Copies of the electronic CRF (eCRF) will be provided for use as source documents and maintained for recording data for each participant enrolled in the study. Data reported in the eCRF derived from source

CONFIDENTIAL

This material is the property of the NYU School of Medicine and Langone Medical Center. Do not disclose or use except as authorized in writing by the study sponsor

documents should be consistent with the source documents or the discrepancies should be explained and captured in a progress note and maintained in the participant's official electronic study record.

Clinical data (including AEs, concomitant medications, and expected adverse reactions data) and clinical laboratory data will be entered into REDCap, a 21 CFR Part 11-compliant data capture system provided by the home institution. The data system includes password protection and internal quality checks, such as automatic range checks, to identify data that appear inconsistent, incomplete, or inaccurate. Clinical data will be entered directly from the source documents.

13.2 Study Records Retention

Study documents will be retained for the longer of 3 years after close-out, 5 years after final reporting/publication, or 2 years after the last approval of a marketing application is approved for the drug for the indication for which it is being investigated or 2 years after the investigation is discontinued and FDA is notified if no application is to be filed or if the application has not been approved for such indication. No records will be destroyed without the written consent of the sponsor, if applicable. It is the responsibility of the sponsor to inform the investigator when these documents no longer need to be retained.

13.3 Protocol Deviations

Protocol deviations must be reported to the local IRB per their guidelines. The site PI/study staff is responsible for knowing and adhering to their IRB requirements. Further details about the handling of protocol deviations will be included in the MOP.

14 Study Finances

14.1 Funding Source

This study will be financed by the Orthopaedics Department of NYU Langone Health.

14.2 Costs to the Participant

There will be no additional costs to the patient as a result of this study.

14.3 Participant Reimbursements or Payments

There will be no participant reimbursement or additional compensation provided on behalf of this study.

15 Study Administration

15.1 Study Leadership

This study, given that it will be a single-center study, will be led by the study PI, [name]. There will be no steering committee.

16 Conflict of Interest Policy

Any investigator who has a conflict of interest with this study (patent ownership, royalties, or financial gain greater than the minimum allowable by their institution, etc.) must have the conflict reviewed by the NYU Langone Conflict of Interest Management Unit (CIMU) with a Committee-sanctioned conflict management

CONFIDENTIAL

This material is the property of the NYU School of Medicine and Langone Medical Center. Do not disclose or use except as authorized in writing by the study sponsor

plan that has been reviewed and approved by the study sponsor prior to participation in this study. All NYULH investigators will follow the applicable conflict of interest policies.

CONFIDENTIAL

This material is the property of the NYU School of Medicine and Langone Medical Center. Do not disclose or use except as authorized in writing by the study sponsor
Interventional Template Version: 11 January 2019
